## 9.2 Sample Size Determination

The sample size calculation was derived for the primary endpoint, the proportion of participants who are in complete remission while off OCS for  $\geq 2$  months at Week 36.

Approximately 60 participants are needed per treatment group to detect a 30% difference between benralizumab and placebo with 90% power. The calculation is based on a 2-sided test and a 5% significance level and assumes a response rate of 50% for benralizumab and 20% for placebo.

There is limited evidence currently available from completed comparative BP trials to date to base the study size assumptions on. However, a mepolizumab Phase 2 trial with a similar

participant population, design, and steroid taper rate reported a low proportion who were relapse free up to 36 weeks (20% versus 33% for mepolizumab versus placebo; [Simon et al 2020](#)). From this study, the assumption that an expected remission rate off steroids at Week 36 would be low, at most 20%, was extrapolated. A 30% improvement in this remission rate was recommended by a panel of BP experts to be at the lower end of what may be clinically meaningful, and so was considered to be a conservative assumption.

A non-binding interim futility analysis will be performed by an Independent Data Monitoring Committee (IDMC) when approximately 36 randomized participants (ie, when approximately 30% of the total amount of statistical information is available) have had the opportunity to complete at least 36 weeks of follow-up. By conducting the interim analysis, the overall power will not be affected substantially. Full details are provided in Section [9.5](#).

### 9.3 Populations for Analyses

Analyses presented in the CSR will be based on the populations as defined in [Table 9](#).

**Table 9 Populations for Analysis**

Population	Description
All participants analysis set	All participants screened for the study, to be used for reporting disposition and screening failures.
Full analysis set	All randomized participants who received at least 1 dose of IP, irrespective of their protocol adherence and continued participation in the study. Participants will be analyzed according to their randomized treatment irrespective of whether or not they have prematurely discontinued, according to the ITT principle. Participants who withdraw consent to participate in the study will be included up to the date of their study termination.
Safety analysis set	The safety analysis set consists of all participants who have received at least one dose of IP. Erroneously treated participants (eg, those randomized to treatment A but actually given treatment B) are accounted for in this analysis set by assigning them to the treatment they actually received. A participant who has on one or several occasions received active IP is classified as active. Safety, and ADA data will be based on this analysis set and for whom any post-dose data are available.
Pharmacokinetic analysis set	All participants who received at least one dose of benralizumab and from whom PK blood samples are assumed not to be affected by factors such as protocol violations (eg, received wrong dose) and who had at least 1 quantifiable serum PK observation post first dose. All PK summaries will be based on this analysis set.
OLE benralizumab analysis set	All participants who start or carry on receiving at least 1 dose of benralizumab after the end of the DB treatment period

ADA, anti-drug antibodies; DB, double-blind; IP, investigational product; ITT, intent-to-treat; OLE, open-label extension; PK, pharmacokinetic.

## 9.4 Statistical Analyses

A comprehensive statistical analysis plan (SAP) will be developed and finalized prior to the primary DBL and will include a more technical and detailed description of the statistical analyses described below. Any deviations from this plan will be reported in the CSR.

This section is a summary of the planned statistical analyses of the primary and secondary endpoints.

All personnel involved in the analyses of the study will remain blinded until the primary DBL and protocol deviations are identified.

Analyses will be performed by AstraZeneca or its representatives.

Categorical variables will be summarized using frequency and percentages, where the denominator for calculation is the underlying analysis set population unless otherwise stated.

Continuous variables will be summarized with descriptive statistics of number of available observations, mean, standard deviation, median, minimum and maximum, and quartiles where more appropriate.

All point estimates will be presented together with 95% confidence intervals (CIs). P-values, corresponding to a 2-sided test, will be presented for comparisons between treatments. Methods for controlling multiplicity across the primary and key secondary endpoints are discussed in Section 9.4.7.

### 9.4.1 General Considerations

The primary analysis will be based on the initial 36-week, double-blind, placebo-controlled phase of the study, and will compare all participants randomized to benralizumab until Week 36 against all participants randomized to placebo until Week 36.

**Table 10** outlines the estimands which will be used for the primary analyses of the primary and key secondary endpoints, with additional detail on each endpoint in the sections below.

**Table 10 Primary and Key Secondary Estimands**

Statistical category	Treatment condition	Endpoint (Population)	Intercurrent event strategy	Population level summary (Analysis)
Primary objective: To compare the clinical efficacy of benralizumab with placebo in participants with symptomatic BP				
Primary	Treatment with benralizumab versus placebo, regardless of IP compliance; restricted medication use indicates treatment failure	Proportion of participants who are in complete remission while off OCS for $\geq 2$ months at Week 36 (FAS)	
 
• Treatment discontinuation – treatment policy
 
• Rescue with OCSa – treatment policy
 
• Restricted medication use – composite (non-responder)
 
• Study withdrawal – composite (non-responder)
 
	Odds ratio and difference in proportion of participants who are responders at Week 36 (logistic regression model)
Secondary objective: To compare the effect of benralizumab with placebo on supportive measures of clinical efficacy in participants with symptomatic BP up to Week 36/up to Week 16				
Key Secondary	Treatment with benralizumab versus placebo, regardless of IP compliance; rescue with OCS and restricted medication use indicate treatment failure	Proportion of participants who remain relapse-free up to Week 36 (FAS)	
 
• Treatment discontinuation – treatment policy
 
• Rescue with OCSa – composite (not relapse free)
 
• Restricted medication use – composite (not relapse free)
 
• Study withdrawal – composite (not relapse free)
 
	Odds ratio and difference in proportion of participants remaining relapse free up to Week 36 (logistic regression model)
Key Secondary	Treatment with benralizumab versus placebo, regardless of IP compliance	Cumulative OCS exposure (mg/kg) from baseline to Week 36 and from baseline to Week 16 (FAS)	
 
• Treatment discontinuation – treatment policy
 
• Restricted medication use – effectiveness (includes OCS dosing up to occurrence of event)
 
• Study withdrawal – effectiveness (includes OCS dosing up to occurrence of event)
 
	Difference in mean cumulative OCS exposure (mg/kg) from baseline to Week 36 and from baseline to Week 16 (MMRM)

**Table 10 Primary and Key Secondary Estimands**

Statistical category	Treatment condition	Endpoint (Population)	Intercurrent event strategy	Population level summary (Analysis)
Key Secondary	Treatment with benralizumab versus placebo, regardless of IP compliance; rescue with OCS and restricted medication use indicate treatment failure	Change from baseline in BPDAI activity score at Week 36, change from baseline in BPDAI-Pruritus score at Week 36 (FAS)	

• Treatment discontinuation – treatment policy

• Rescue with OCSa – composite (LOCF)

• Restricted medication use – composite (LOCF)

• Study withdrawal – hypothetical (multiple imputation)

	Difference in mean change from baseline in BPDAI activity score/BPDAI-Pruritus score at Week 36 (ANCOVA)

a Rescue with OCS is defined as needing to increase OCS dose after previously having achieved disease control.

ANCOVA, analysis of covariance; BP, bullous pemphigoid; BPDAI, bullous pemphigoid disease area index; FAS, full analysis set; IP, investigational product; LOCF, last observation carried forwards; MMRM, mixed-effect model for repeated measures; OCS, oral corticosteroids.

The amount of missing data for this study is expected to be low, as participants who prematurely discontinue IP will be asked to come in for all visits and complete all study assessments up to the end of the study. Any participant with missing data at a specific time point will be considered as a non-responder at that time point.

Further estimands will be specified for the primary and key secondary endpoints to carry out sensitivity analyses for assessing the robustness of results. These sensitivity analyses will explore different methods for handling intercurrent events and different assumptions for missing data. Further description is given in Section 9.4.8 and will be fully specified in the SAP.

All analyses for the OLE endpoints will be descriptive, as no placebo-control data will be available for this period. Consequently, no hypothesis testing will be performed.

Demography and baseline characteristics will be summarized by treatment for the FAS. If there are major differences between the FAS and the safety analysis set, the summaries will be repeated and presented for the safety analysis set.

## 9.4.2 Efficacy Analyses

### 9.4.2.1 Primary Analysis Method

#### **Proportion of participants who are in complete remission and have taken no oral corticosteroids for $\geq 2$ months at Week 36**

The primary endpoint is a binary response whereby participants will be classified as responders if they are in complete remission while off OCS for  $\geq 2$  months at Week 36. Otherwise, participants will be classified as non-responders.

The estimand strategy is outlined in Table 10 above. Intercurrent events (use of restricted medications, study withdrawal) are unfavorable outcomes and will be handled with a composite strategy whereby participants experiencing these events prior to Week 36 will be considered as non-responders in the analysis. Likewise, participants with missing data at Week 36 for any other reason will be considered as non-responders. However, for this endpoint, if a participant needs to increase OCS after previously achieving disease control but still tapers and achieves the remission criteria by Week 36, this will count as response in the analysis. It is considered unlikely that this situation would emerge often, but given the clinical relevance of still being able to achieve remission and that OCS use is built into the remission definition, it is considered appropriate to count this situation as response in the analysis.

For the primary analysis, a logistic regression model will be fitted to the primary endpoint using a logit link function. The model will include treatment, baseline disease severity (moderate; severe) and time of BP diagnosis (ie, participants with newly diagnosed BP versus participants with a previous diagnosis of BP who have relapsed) as categorical covariates.

(Note that participants will be classified as severe based on a cut-off of 56 points for baseline BPDAI activity score.) The effect of adding further covariates into the model, such as age and region, may also be assessed as a sensitivity analysis if any potentially significant imbalances occur in the set of baseline characteristics.

The model will be used to estimate the proportion of responders for benralizumab and placebo, the difference between these proportions (benralizumab – placebo), a rate ratio (benralizumab/placebo) and an odds ratio, with corresponding 95% confidence limits. A p-value, corresponding to a 2-sided test, will be presented to compare the benralizumab and placebo treatment groups. Note that if the logistic regression model does not converge to a solution due to low response rates in certain categories, the endpoint will be analyzed using a Cochran–Mantel–Haenszel test.

To support this analysis, the observed proportion of responders will be summarized using descriptive statistics by treatment group and each scheduled visit up to Week 36.

#### **9.4.2.2 Analysis Methods for Key Secondary Efficacy Variables**

##### **Proportion of participants who remain relapse-free up to Week 36**

The proportion of participants who remain relapse-free up to Week 36 will be analyzed as a binary response variable, where participants who remain relapse-free throughout the study up to Week 36 will be considered responders, but otherwise participants will be considered non-responders. Relapse is defined as the appearance of: 3 or more new lesions per month (blisters, eczematous lesions, or urticarial plaques); or at least one large ( $> 10$  cm diameter) eczematous lesion or urticarial plaques that do not heal within 1 week; or the extension of established lesions or daily pruritus in participants who have achieved disease control.

The estimand strategy is outlined in [Table 10](#) above. Intercurrent events of rescue use with OCS after having previously achieved disease control, restricted medication use, and study withdrawal are unfavorable outcomes and will be handled with a composite strategy whereby participants experiencing these events prior to Week 36 will be considered as non-responders (ie, not relapse-free) in the analysis. Likewise, participants with missing data at Week 36 for any other reason will be considered as not-relapse free.

For the primary analysis of the proportion of participants relapse-free at Week 36, a logistic regression model will be fitted using a logit link function. The model will include treatment, baseline disease severity (moderate or severe, with a BPDAI activity score of 56 points used as the threshold between moderate and severe) and time of BP diagnosis (ie, participants with newly diagnosed BP versus participants with a previous diagnosis of BP who have relapsed) as categorical covariates.

The model will be used to estimate the proportion who are relapse-free for benralizumab and placebo, the difference between these proportions (benralizumab – placebo), a rate ratio

(benralizumab/placebo), and an odds ratio, with corresponding 95% confidence limits. A p-value, corresponding to a 2-sided test, will be presented to compare the benralizumab and placebo treatment groups. Note that if the logistic regression model does not converge to a solution due to low response rates in certain categories, the endpoint will be analyzed using a Cochran–Mantel–Haenszel test.

As supportive analyses to explore the timing of relapse events, the time to first BP relapse will also be analyzed, where time to first relapse is defined as the earliest time after randomization that any of the relapse criteria are met. This analysis will use a log-rank test stratified by baseline disease severity (moderate; severe) and time of BP diagnosis (ie, participants with newly diagnosed BP versus participants with a previous diagnosis of BP who have relapsed). A p-value, corresponding to a 2-sided test, will be presented to compare the benralizumab and placebo treatment groups. A Cox-proportional hazards model will be used to estimate the hazard ratio and its 95% CI. The median time to first relapse will be estimated from the Kaplan-Meier curves for the benralizumab and placebo treatment groups.

### **Cumulative OCS exposure (mg/kg) from baseline to Week 36 and from baseline to Week 16**

Two cumulative OCS exposure endpoints are defined: the cumulative OCS exposure over the 36-week double-blind period, and the cumulative OCS exposure over the first 16 weeks of the study. Each of these endpoints will be assessed from a mixed-effect model for repeated measures (MMRM), examining each participant's cumulative OCS exposure in 4-week periods. The cumulative exposure over the 36 (and 16) weeks will be estimated as the sum over the relevant 4-week periods from the MMRM model. This analysis method was selected to utilize all available data in the situation of any participants dropping out prior to 36 weeks. This ensures that any such participants can still contribute to the analysis for the period they remain in the study, without needing to make potentially implausible imputation assumptions around future OCS exposures in these situations (eg, carrying forward a high last observation of 0.75 mg/kg/d, which would not be a feasible dose to maintain for a 36-week period).

As highlighted in [Table 10](#), the intercurrent events of restricted medication use and study withdrawal will be handled with an effectiveness strategy, including all available data in the MMRM model until the occurrence of such events. As described above, this avoids needing to make potentially implausible imputation assumptions that a composite strategy would involve. Likewise, use of a treatment policy strategy is also not considered appropriate, as use of restricted medications would confound future OCS use. For example, if OCS were discontinued to receive another treatment due to lack of response or intolerance to OCS, the treatment policy approach would show a low cumulative OCS dose, which is a positive outcome and does not fairly represent the overall picture. Note that the list of intercurrent events does not include rescue with OCS (ie, increases in OCS dose after achieving disease

control), as by definition of the endpoint, increases in OCS dosing will be reflected in the cumulative OCS dose.

The model will include cumulative OCS exposure (mg/kg) as the dependent variable (calculated for each participant over 4 weekly intervals up to Week 36); treatment, 4 weekly interval, baseline disease severity and time of BP diagnosis as categorical covariates; treatment-by-4 weekly interval as an interaction term. The inclusion of baseline OCS dose as a covariate will also be considered. An unstructured variance-covariance matrix will be used to model within-participant errors, and the Kenward-Roger approximation will be used to estimate denominator degrees of freedom and to adjust standard errors. (If the model fails to converge, alternative variance-covariance models will be tried in the following order: Toeplitz, first-order regressive, compound symmetry.) For each 4 weekly interval and for the sum of the 4-weekly intervals over the whole of the 36-week treatment period, and for the sum of the 4-weekly intervals over the initial 16-week treatment period, the model will be used to estimate the mean cumulative OCS exposure (mg/kg) for each treatment group and the difference versus placebo, with corresponding 95% confidence limits. P-values, corresponding to 2-sided tests, will be presented to compare the benralizumab and placebo treatment groups for each interval, including the whole of the 36-week treatment period and the initial 16-week treatment period.

To support this analysis, observed means will be summarized using descriptive statistics by treatment group and each 4 weekly interval, are for the whole of the 36-week treatment period and the initial 16-week treatment period.

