#### 4.1.1 Screening Period

After obtaining informed consent, all participants will enter a screening period. The screening period is targeted to last 0 to 4 days depending upon the study assessment requirements (eg, there may be delays beyond 4 days awaiting confirmatory biopsy and serology results). During the screening period, participants may continue their topical or oral corticosteroids; however, any topical corticosteroids will need to be discontinued at randomization.

The following will occur during this period:

- Assessment of participant eligibility based on inclusion/exclusion criteria
- Assessment of BP
- Recording of medical history and concomitant medications
- Clinical and laboratory evaluations, including biopsies

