#### 4.1.2 Double-blind Treatment Period

Approximately 120 eligible participants will be randomized 1:1 at baseline (Visit 2), to receive either benralizumab or placebo every 4 weeks (Q4W) by subcutaneous (SC) injection.

The randomization will be stratified by disease severity and time of BP diagnosis (participants with newly diagnosed BP; participants with a previous diagnosis of BP who have relapsed). Bullous pemphigoid disease area index (BPDAI) activity score will be used to assess disease severity, whereby participants with a score greater than or equal to 56 points will be classified as severe. The double-blind treatment period for each participant will last for 36 weeks.

Participants will receive a loading dose of either 60 mg benralizumab or placebo, administered as 2 SC injections at Visit 2. After 4 weeks, participants will receive 30 mg benralizumab or placebo Q4W per their initial randomization until the end of the double-blind treatment period. Starting at Visit 2, participants will also receive OCS 0.5 mg/kg/day until BP disease control is achieved. In participants who do not achieve disease control, the OCS dose can be increased (eg, 0.75 mg/kg; [\(Feliciani et al 2015\)](#) to achieve disease control. The steroid doses and time necessary to achieve disease control of BP may vary between participants.

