3 PRIMARY AND SECONDARY VARIABLES

3.1 General definitions

3.1.1 Baseline definition

For efficacy, the last recorded value on or prior to the date of randomization will serve as the baseline measurement. If time is collected and relevant for the analysis, the assessment performed the same day but at a time prior to randomization will be included in the baseline definition.

For safety and PK, the last recorded value on or prior to the first dose of study treatment will serve as the baseline measurement. If time is collected, the assessment performed the same day but at a time prior to the first dose of study treatment will be included in the baseline definition.

When time of assessment is not recorded or missing, it is assumed that assessments recorded on the date of randomization (or the date of the first dose of study treatment, depending on the endpoint) were performed prior to randomization (or dosing), except in cases of protocol specified post-dose assessments. If there is no value prior to randomization (or dosing), then the baseline value will not be imputed and will be set to missing.

No data known to be collected post first dose will be used in determining the baseline value, unless otherwise specified.

For physical examinations baseline data will be collected at Visit 2 before first dose of IP.

For the Peak Pruritus Numeric Rating Scale (NRS), which is calculated as the average of daily scores over 7 days, change will be assessed by comparison to the assessments on the date

when disease control was recorded and on the 6 days after. Further details on scoring for PROs will be provided in Section [3.6.1](#).

Additional analyses for the participants who switch from placebo to benralizumab at Week 36 may be performed where the baseline value is set to the last recorded value prior to starting benralizumab (ie, likely the Week 36 measurement) to obtain an assessment of the changes occurring while receiving benralizumab.

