Race (White, Asian, Other)

Region (Europe, North America, Rest of World)

OCS dose at randomization (≤ 0.5 mg/kg/day, > 0.5 mg/kg/day; if suitable distribution of data)

Baseline blood eosinophils ($<$ median, \geq median)

OCS dose at disease control (≤ 0.5 mg/kg/day, > 0.5 mg/kg/day; if suitable distribution of data)

OCS dose at disease control will be calculated for each participant as the dose recorded by the Investigator as per Section 3.1.5.1 on the day before the clinical assessment of disease control.

Stratification and subgroup variables will be based on eCRF data, and not data entered in IxRS. If eCRF data is missing for disease severity or time of BP diagnosis, the IxRS data will be used in the analysis.

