4.2.2 Demography data and participant characteristics

Demography and baseline characteristics will be summarized by treatment group and overall in the FAS, using frequency and percentages (for categorical variables) and descriptive statistics of n, mean, standard deviation, median, minimum, and maximum, and where appropriate first quartile and third quartile (for continuous variables). If there are major differences in the number of participants between the FAS and safety analysis set, these summaries will be repeated for the safety analysis set. These summaries will be presented for reporting of the double-blind treatment period at primary DBL.

Various baseline characteristics will also be summarized. These include participant characteristics (ie, age at informed consent [as continuous and categorical variable in 3 categories < 65 years, ≥ 65 years and < 75 years, ≥ 75 years], weight, height, BMI, gender, ethnicity, race, region) and disease characteristics (ie, disease severity, time of BP diagnosis, current active disease duration at screening [as collected in the eCRF in 5 categories ≤ 1 month, >1-≤ 3 months, >3-≤ 6 months, >6-≤ 12 months, > 12 months], number of BP relapses the last 2 years before screening [as collected in the eCRF in 4 categories 0, 1, 2, ≥ 3], clinical presentations [including presence of blisters, pruritus, erosions, erythema, urticaria plaques], anatomic location, OCS dose at randomization [as continuous and categorical variable in 4 categories ≤ 0.25 mg/kg/day, > 0.25 mg/kg/day and ≤ 0.50 mg/kg/day, > 0.50 mg/kg/day and ≤ 0.75 mg/kg/day, > 0.75 mg/kg/day], baseline blood eosinophil count [as continuous and categorical variable in 4 categories < 150 cells/µL, ≥ 150 cells/µL and < 300 cells/µL, ≥ 300 cells/µL and < 450 cells/µL, ≥ 450 cells/µL], baseline total serum IgG directed against auto-antigens BP-180, baseline total serum IgG directed against auto-antigens BP-230).

Age will be derived from the date of informed consent-date of birth, rounded down to the nearest integer. For participants in countries where date of birth is not recorded, the age as recorded in the eCRF will be used.

Medical and surgical histories will be coded using the most recent version of the MedDRA that will have been released for execution at AstraZeneca/designee per the Data Management Plan and will be summarized by MedDRA Preferred Term (PT) within MedDRA System Organ Class (SOC).

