4.2.7.2 Cumulative OCS exposure (mg/kg) from baseline to Week 36 and from baseline to Week 16

Cumulative OCS exposure (mg/kg) from baseline to Week 36 and from baseline to Week 16 will be calculated for each participant over 4 weekly intervals. More details on derivation rules and intercurrent events are given in Section 3.3.2.

The null hypothesis is: the mean for benralizumab is equal to the mean for placebo. Whereas, the alternative hypothesis is: the mean for benralizumab is not equal to the mean for placebo. That is:

$$H_0: \text{Difference in means (benralizumab} - \text{placebo}) = 0$$

$$H_1: \text{Difference in means (benralizumab} - \text{placebo}) \neq 0$$

This endpoint will be analysed by a MMRM model.

The cumulative exposure over the 36 (and 16) weeks will be estimated as the sum over the relevant 4-week periods from the MMRM model. This analysis method was selected to utilize all available data in the situation of any participants dropping out prior to 36 weeks. This ensures that any such participants can still contribute to the analysis for the period they remain in the study, without needing to make potentially implausible imputation assumptions around future OCS exposures in these situations (eg, carrying forward a high last observation of 0.75 mg/kg/d, which would not be a feasible dose to maintain for a 36-week period).

The model will include cumulative OCS exposure (mg/kg) as the dependent variable; treatment, 4 weekly interval, baseline disease severity and time of BP diagnosis as categorical covariates, treatment-by-4 weekly interval as an interaction term.

An unstructured variance-covariance matrix will be used to model within-participant errors, and the Kenward-Roger approximation will be used to estimate denominator degrees of freedom and to adjust standard errors. If the model fails to converge, alternative variance-covariance models will be tried in the following order: Toeplitz, first-order regressive, compound symmetry.

For each 4 weekly interval and the whole of the 36-week treatment period, and for the initial 16-week treatment period, the model will be used to estimate the mean cumulative OCS exposure (mg/kg) for each treatment group and the difference versus placebo, with corresponding 95% confidence limits.

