Results will be presented in terms of least square (LS) means of cumulative OCS exposure (mg/kg), treatment differences in LS means of cumulative OCS exposure (mg/kg), 95% CI and p-values for all scheduled visits. The cumulative OCS exposure (mg/kg) at Week 36 and Week 16 will be of primary interest. The LS means will be calculated using the OM option in the LSMEANS statement and the treatment-by-visit interaction to provide a LS means estimate for each scheduled visit. The LS means with 95% CIs will also be presented for each treatment group by scheduled visit.

P-values, corresponding to 2-sided tests, will be presented to compare the benralizumab and placebo treatment groups for each interval, including the whole of the 36-week treatment period and the initial 16-week treatment period.

The following SAS code is given as an example:

```
lsmestimate Treatment * 4WeeklyInterval  
  
'Treatment 1: 16 weeks' 0 0 0 0 0 0 0 0 0  
                      1 1 1 1 0 0 0 0 0,  
'Treatment 0: 16 weeks' 1 1 1 1 0 0 0 0 0  
                      0 0 0 0 0 0 0 0 0,  
'Diff: 16 weeks'    -1 -1 -1 -1 0 0 0 0 0  
                      1 1 1 1 0 0 0 0 0,  
'Treatment 1: 36 weeks' 0 0 0 0 0 0 0 0 0  
                      1 1 1 1 1 1 1 1 1,  
'Treatment 0: 36 weeks' 1 1 1 1 1 1 1 1 1  
                      0 0 0 0 0 0 0 0 0,  
'Diff: 36 weeks'    -1 -1 -1 -1 -1 -1 -1 -1 -1  
                      1 1 1 1 1 1 1 1 1  
/ om cl;
```

To support this analysis, observed means will be summarized using descriptive statistics by treatment group and 4 weekly interval, including the whole of the 36-week treatment period and the initial 16-week treatment period. Observed means will be also plotted by treatment group and 4 weekly interval.

To explore the uniformity of the detected overall treatment effect, the model might also be fitted considering OCS dose at randomization and its interaction with treatment as additional covariates.

The set of intercurrent events for this estimand and the imputation approach are detailed in Section 3.3.2. Since any BP relapses are expected to be treated with OCS (which is incorporated in the endpoint definition), the use of restricted medications which would result in exclusion of data beyond that point are expected to be infrequent. Therefore, the amount of missing data is expected to be low and is considered not likely to impact the results.

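### The main model for cumulative OCS exposure has no baseline measure of steroid use; adding pre-study OCS dose before unblinding may gain some precision at almost no cost

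*Protocol*

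**What the plan says.** Protocol 9.4.2.2 lists the terms of the MMRM for cumulative OCS exposure and then adds "The inclusion of baseline OCS dose as a covariate will also be considered". SAP 4.2.7.2 fixes the main model as "treatment, 4 weekly interval, baseline disease severity and time of BP diagnosis as categorical covariates, treatment-by-4 weekly interval as an interaction term". Later in the same section, under exploring uniformity of the treatment effect, it says that "the model might also be fitted considering OCS dose at randomization and its interaction with treatment as additional covariates". SAP Section 6 explains why disease severity left the BPDAI activity ANCOVA but does not mention baseline OCS dose.

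The information is collected. The protocol's Schedule of Activities records OCS dose from Visit 1, and protocol 6.5 lists background OCS among the medications to be recorded. SAP 4.2.2 tabulates "OCS dose at randomization [as continuous and categorical variable in 4 categories" among the baseline characteristics, and SAP 4.1.2 lists it as a subgroup variable.

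Three passages bear on what the variable means. Protocol 4.1.1: "During the screening period, participants may continue their topical or oral corticosteroids". Protocol 4.1.2: "Starting at Visit 2, participants will also receive OCS 0.5 mg/kg/day until BP disease control is achieved". SAP 3.1.1, for efficacy: "the last recorded value on or prior to the date of randomization will serve as the baseline measurement".

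**The concern.** The BPDAI activity ANCOVA adjusts for its own continuous baseline. When SAP Section 6 removed a redundant term there, it kept the continuous baseline and dropped the binary factor. The cumulative OCS model has no counterpart: its only baseline terms are two binary factors, severity and newly diagnosed versus relapsed. SAP 4.1.2 separates participants who relapsed on OCS from those who relapsed off OCS, but the MMRM does not use that distinction either.

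Pre-study dose is a plausible predictor of later steroid need, since escalation, rescue and slow taper all count in this endpoint. If it does predict, leaving it out widens the confidence interval for tests three and six. Test three matters most, because failure there ends confirmatory testing of the three endpoints below it. The SAP's planned sample is 100 rather than the protocol's 120, and no power is stated for this endpoint.

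**Working it through.** **The plan's own figure.** The only sizing in the documents is for the primary endpoint: 50% versus 20%, two-sided 5%, with 60 per group at 90% power (protocol 9.2) and 50 per group at 85% (SAP 1.3). Continuity-corrected power is the normal probability below

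z = (0.30 − 1/n − 1.96·√(2·0.35·0.65/n)) / √((0.25 + 0.16)/n).

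- n = 50: z = (0.280 − 0.187)/0.0906 = 1.03, power 0.848.
- n = 60: z = (0.2833 − 0.1707)/0.0827 = 1.36, power 0.914.

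The stated figures reproduce. They say nothing about cumulative OCS exposure, for which no SD, effect size or power is given.

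**Effect of the covariate.** Let rho be the partial correlation of pre-study OCS dose with summed exposure, given treatment, severity and time of diagnosis. Treating the summed contrast as a single outcome with complete data, the residual variance is multiplied by 1 − rho². Adding one term to a four-parameter model with 2n = 100 takes the residual degrees of freedom from 96 to 95, so

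SE ratio = √((1 − rho²)·96/95).

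Equivalent sample-size gain = 1/(SE ratio)² − 1. The power column assumes 50 per group and an effect of 0.56 SD, chosen to give 80% power without the covariate.

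| rho (assumed) | √(1 − rho²) | SE ratio with df cost | Equivalent gain in n | Power |
|---|---|---|---|---|
| 0.1 | 0.995 | 1.000 | 0% | 80.0% |
| 0.2 | 0.980 | 0.985 | 3.1% | 81.2% |
| 0.3 | 0.954 | 0.959 | 8.7% | 83.2% |
| 0.4 | 0.917 | 0.921 | 17.8% | 86.0% |
| 0.5 | 0.866 | 0.871 | 31.9% | 89.6% |

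With 60 per group the results are almost the same. The gain depends on rho², so the sign of the relation does not matter.

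**Which dose.** Everyone starts study OCS at 0.5 mg/kg/day at Visit 2 (or higher if required, per the protocol synopsis), and Visit 2 is the randomization visit. The efficacy baseline may be a value from the randomization date, and SAP 3.1.1 treats same-day values without a time as earlier. SAP 3.1.5.1 counts a participant as on OCS from the start date inclusive. Read together, these could make OCS dose at randomization the study starting dose, which is about the same for most participants and would give a rho near zero. Only the dose taken before study OCS starts can vary widely.

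**Size of the model.** The example code in SAP 4.2.7.2 has nine 4-weekly intervals. A dose-by-interval interaction gives nine interval-specific slopes, so the slope for the 16-week or 36-week sum is estimated freely. For each summed contrast the cost remains about one degree of freedom.

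**The case against.** The case for leaving the model alone is reasonable. The protocol promised only to consider the term. The SAP then settled the matter with a fully pre-specified model and an optional fit, so a reader who inferred an unreported departure from the protocol would go too far: Section 6 was not obliged to list it. A reader might also infer bias or a false-positive risk. Neither follows, because in a randomized comparison omitting a baseline covariate costs efficiency at most.

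Nor do the documents show that precision is being lost. They give no correlation and no distribution for this variable. The two-level split in SAP 4.1.2, "OCS dose at randomization (≤ 0.5 mg/kg/day, > 0.5 mg/kg/day; if suitable distribution of data", is conditional, and the four categories in SAP 4.2.2 are display bands, so neither proves that a wide spread is expected. The common start and protocol taper may weaken any link with prior dose. Time of diagnosis and severity already carry some of the same information, and coding untreated participants as zero places newly diagnosed people at the low end even though they may need substantial steroid.

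All of this stands as a limit on size: at rho of 0.2 or less the gain is negligible. It is not an argument against the change, because the loss if rho is zero is about one degree of freedom. The optional fit is no substitute: it includes a treatment interaction, addresses uniformity of effect, and is not the confirmatory test.

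**Conclusion.** The point holds as a matter of efficiency and pre-specification. The protocol raised baseline OCS dose as a covariate, the SAP's main model omits it without a recorded reason, and the model for tests three and six has no baseline measure of steroid use.

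The possible gain in standard error runs from nothing at rho 0.1 to about 8% at rho 0.4. On an assumed 80% base that is 0 to 6 percentage points of power. These figures rest on an assumed rho, an assumed effect size and complete data, and nothing in the documents selects a value. The conclusion is that precision may be lost, not that it is. It also depends on using the pre-study dose; the Visit 2 starting dose would add little or nothing. This is a free improvement rather than a required correction.

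**What to change.** Before unblinding, add two fixed terms to the main MMRM of SAP 4.2.7.2:

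- pre-study OCS dose as a continuous covariate, in mg/kg/day prednisone equivalent, defined as the last dose before study OCS starts at Visit 2 and set to zero if none;
- its interaction with the 4-weekly interval.

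State explicitly that the Visit 2 study starting dose is not the covariate. The conversion table in SAP 3.1.5.3 and baseline weight already supply the units, and the treatment contrasts for 16 and 36 weeks need no change. If the sponsor prefers to keep the current model, one sentence in Section 6 should give the reason.

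The cost is a few lines of SAP text with no new data collection. SAP 8.1.8 already foresees a SAP update before primary database lock. Statistically, the cost is about one degree of freedom per summed contrast, plus nine slopes in a model with an unstructured covariance; the convergence fallbacks already planned in SAP 4.2.7.2 apply unchanged.
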